Official Title of the study: The Omnibus Satiety Metric (OmniSaM)

Date of the document: 1 March 2019

Full study protocol and statistical analysis plan

Contents

- 1. Participant Flow
- 2. Baseline Characteristics
- 3 Outcome Measures
- 4. Adverse Event Information
- 5. Limitations and Caveats
- 6. Certain Agreements
- 7. Results Point of Contact

1. Participant Flow

Recruitment Details. Participants were recruited via convenience sample via the website www.forsøgsperson.dk . The recruitment started oct 2017 and lasted around approx.

Pre-assignment Details. Via a phone meeting we first assess if the volunteers fulfill the inclusion-exclusion criteria. Those who meet the initial criteria for inclusion will participate in an information meeting where information about procedures will be delivered and participants can ask questions. Those who agree to participate in the study will give written consent, deliver a blood sample to be analyze for: hemoglobin, liver and kidney function and inflammatory state, and weight, height and blood pressure will be measured, to ensure the recruited people meet all the inclusion and exclusion criteria. These criteria are listed in the main clinical trials document.

Enrollment (total, anticipatory). Total whom started the study 28; Anticipated completion of all four test days 25; Fully completion of all four test days 23; Excluded from analyses 5 Allocation (randomized). This is a single arm study in which all conditions of a 2x2 factorial design and allocated to the same group in a randomized order.

Follow-up (immediately after intervention). There is no follow up.

Arm/Group Information. There is 1 arm in the study.

Arm/Group Description. All participants in this single arm study undergo a dietary intervention, comprising the 2x2 factorial design in which they are tested under four conditions in which only the dietary preload changes.

- 1. high protein2carb high calorie
- 2. high protein2carb low calorie
- 3. low protein2carb high calorie
- 4. low protein2carb low calorie

Period(s). There is only one stage in the study, comprising the four test days, one for each of the experimental conditions

Period Title. Overall Study. **Started.** 28 started the study. **Completed.** 23 finished the study.

Milestone Title. There are no follow ups so therefore no milestones.

Reason Not Completed Type. The reasons for not completing the study included only the following, and were fully recorded: Metal thread behind front teeth (1); Excluded by project staff due to frivolous attitude towards the study (1); Physiological hindrance of drawing blood from subject (1); Blood sampling not possible (2); Personal issues without the possibility of rescheduling (1)

2. Baseline Characteristics

Arm/Group Information. Baseline characteristics will be computed in the form of standard summary statistics (means, standard deviations, Bayesian credibility intervals) $\textbf{Baseline Measure Information.} \ \textbf{A} \ \text{group of demographic characteristics will be measured in}$ the study, including: age; gender; weight; height; educational level; income;

Baseline Measure Title. Age: Continuous (years); Gender: Categorical (female, male); Weight: Continuous (kg); Height Continuous (meter); Educational level: Categorical (lower secondary, higher secondary, higher secondary with trainee, short-length higher education, mediumlength higher education, long-length higher education); Income: Categorical (< 100.000 Dkkr, 100.000-199.999 Dkkr, 200.000-299.999 Dkkr, 300.000-399.999 Dkkr, 400.000-599.999 Dkkr, 600.000-799.999 Dkkr, ≥ 800.000 Dkkr, do not wish to inform)

Measure of Dispersion. Standard Deviation, Interquartile ranges, Range

3. Outcome Measures

 $\label{lem:composition} \textbf{Outcome Measure Information.} \ \text{The primary outcome is the energy consumed in the ad}$ libitum meal.

Outcome Measure Type. Primary Outcome Measure Title. Energy consumed

Outcome Measure unit. kJ

Outcome Measure Time Frame. There will be four such measurements per participant, one for each condition. These are taken at the end of the experimental testing day Overall Number of Participants Analyzed. There will be data analysed from 23 participants.

Measure Type. Means Measure of Dispersion/Precision. Standard Deviation and Bayesian central credibility intervals Outcome Data. The measurement value(s) for each outcome measure cannot obtain right now since data collection has not finished yet.

Comparison Group Selection. There is only 1 group.

Statistical Testing.

Statistical modelling of multimodal metric

A Bayesian linear regression will be implemented in JASP software, with the primary outcome of energy consumption as the dependent variable. The regressor variables will be variables derived from all three data modalities (described below). This regression model computes all possible combinations of regressors, with each combination specified as a separate model and assigned an equal prior probability. The regressors to be tested are defined operationally as follows: we compute a Principal component analysis (PCA) to identify the components within the data necessary to explain 95% of the variance in the data, with the PCA performed independently for the three modalities of data, brain, blood and behavior. For all of these different models, Bayes Factors can be computed comparing each model against the best model, or alternatively against the null model. The null model is taken to include all covariates not included in the neuroimaging data, subjective report data, or endocrine and metabolite data. Inclusion probabilities will be computed for all regressors, which allows us to infer Bayes factors that indicate the evidence for models including each regressor against all models that do not. This indicates how much the data favors the inclusion of the regressor in the best model. Inclusion probabilities and their associated Bayes factors will be computed for all regressors and their groupings into the three data modalities. This affords inference into the how much the data favors the inclusion of a particular data modality. Bayes factors will also be computed between data modalities, to evaluate the relative importance of each modality in predicting energy consumption. The regressors can also be grouped according to timepoint, affording comparison of inclusion probabilities between distant and proximal times to the point of consumption.

Statistical modelling of subjective measures

In modelling the subjective reports of appetitive sensations we will perform the following procedures: To address the question of how well subjective measures predict energy intake we will perform a Partial Least Squares analyses, to find the multidimensional direction in appetite sensation space, that explains the maximum variance in energy intake space. To isolate the subset of subjective factors that are best predictive of energy intake we will perform a Bayesian Linear regression with subjective reports and time as regressors, and with energy expenditure, weight and BMI as covariates. To address the question of between preload effects on subjective reports of hedonic- and appetite ratings and energy intake, and the discriminability of the different appetite ratings, we will perform a repeated measures 2way ANOVA, with both preload dimensions and time as independent/explanatory variables and hedonic, appetite and intake data as dependent/response variables. The repeatedmeasure factor will be the within-subject factor. Post hoc pairwise multiple-comparisons will be used as follow-up tests to compare every group mean.

Statistical modelling of neural measures

The aim of neuroimaging analysis is to delineate the interoceptive neural systems underpinning satiety, and its interface with behavioral and endocrine systems. Broadly we hypothesise that tonic & food cue-evoked activity in viscerosensory & visceromotor networks, will be predictive of next-meal energy intake, specifically in Hypothalamus & Insula and more broadly in regions of interest: ACC, OFC, SGC, PBN, NTS, amygdala, striatum. We will engage in exploratory data analysis by mapping the neural modulations caused by post-prandial endocrine dynamics. Finally we will extract key features of data from regions of interest to assess how neural activity can predict energy intake. For the functional neuroimaging data, a multiple linear regression model will be constructed via the software Statistical Parametric Mapping. The onset of food and object images will be modelled as stimulus onsets using $standard\ methods,\ convolving\ stick\ functions\ representing\ stimulus\ onsets\ with\ hemodynamic$ response functions. Regressors of interest will include food images classified according to high or low energy density, and objects. Resting state data will be modelled according to standardized pipelines. We will compute the main effect of caloric density of food cues. We will compute the Parametric modulations of blood and subjective covariates on these caloric density responses. We will compute the main effect of endocrine and subjective covariates as slow varying modulators of resting activity. Multivariate Bayesian decoding will be performed on regions of interest to ask which brain regions decode onto endocrine responses, subjective responses, and ultimately energy intake.

Statistical modelling of endocrine responses

In modelling the endocrine responses we will focus on 2 physiological modalities; appetite sensation (outcome=energy intake) and nutrient sensing (outcome=hormone responses). 1. Appetite sensation: To address the question of how well endocrine responses predict energy intake we will perform a linear regression models with energy intake as dependent variable and AUC of endocrine metabolic marker and energy expenditure (calculated from height and weight) as covariates (and subject id as random effect). A regression model will be performed for each of the different endocrine markers to find the marker that explains the maximum variance in energy intake.

In addition, we will perform a Bayesian linear regression (as described in preceding section), with energy intake as dependent variable. The regressors of interest will be based on area under the curve metrics computed from all of the endocrine and metabolic markers obtained from the blood sampling including GLP1, Ghrelin, PYY, CCK, glucose, insulin.

2. Nutrient sensing: To address the question of between preload effects on endocrine responses we will perform a repeated measures 2-way ANOVA with AUC of endocrine marker as dependent variable and both preload dimensions as independent fixed effects and individual subject id as an independent random effect. Post hoc pairwise multiple-comparisons will be used as follow-up tests to compare every group mean.

4. Adverse Event Information

Time Frame. Possible adverse events can include fainting at the point of drawing blood. This is monitored by two researchers at all times, where the participant is vulnerable to fainting. Adverse Event Reporting Description. We will add relevant information about adverse event after finishing the study

5. Limitations and Caveats

There may be several limitations or caveats. First, it is possible that the dietary intervention does not impact on energy consumption hours later. The dietary intervention is primarily used as a manipulation to drive variation in consumption. As long as consumption has variance across and within participants, then the main goal of using the data modalities to predict satiety is still achievable. Second, it is possible participants do not comply with instructions prior to their experimental day. This will be evident in the blood measures, indicating for instance if they have not fasted. Non-compliance could be evident in their tracker activity, for instance if they have engaged in extreme activity prior to testing. However not all such cases can be inferred from these measures.

6. Certain Agreements

Are all Pls Employees of Sponsor? No. There is one sponsor-investigator and none of the other principal investigators are employed by the sponsor.

Results Point of Contact

Name. [name] [name], PhD Position title: Post Doc

Organization Name. University of Aarhus

[contact]

Email. [contact]

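### Only the 23 four-day completers are analysed, so any test days from the 5 excluded starters are lost even to analyses that need neither four days nor blood nor scans

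*Combined protocol and SAP*

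**What the plan says.** Section 1 (Participant Flow, Enrollment) counts the starters as "Total whom started the study 28" and gives the expected number of completers as "Anticipated completion of all four test days 25". The outcome is then recorded as "Fully completion of all four test days 23; Excluded from analyses 5". Section 3 (Outcome Measures) says of the primary outcome, energy eaten at the ad libitum meal, "There will be data analysed from 23 participants", and of its timing "There will be four such measurements per participant, one for each condition". The analysis set is therefore the people with all four days.

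The reasons for not completing are presented as exhaustive and fully recorded. The first is a dental one, "Metal thread behind front teeth (1)". The next is a removal by staff, worded as "Excluded by project staff due to frivolous attitude towards the study (1)". Three failures to obtain blood come after it, entered as "Physiological hindrance of drawing blood from subject (1); Blood sampling not possible (2)". The last is one case of personal issues that could not be rescheduled.

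None of the modelling subsections in section 3 defines its own analysis set. No missing-data method is given, and no sensitivity analysis on the set is planned.

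**The concern.** A single completers-only set applies the strictest requirement of the study (four days, with every procedure tolerated) to analyses that do not share it. Under the subjective-measures heading, the partial least squares analysis and the Bayesian regression of intake on ratings use neither blood nor scan data. A person whose blood could not be drawn might still have ratings and a test meal.

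Two things are at stake. The first is some precision in a study of 23 people. The second is selection after enrolment: the analysed sample becomes conditional on tolerating every procedure and, for one person, on a staff judgement of attitude. No criterion, timing or decision-maker is given for that removal, and nothing says whether it was made without sight of the person's data.

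**Working it through.** **Reproducing the plan's count.** Starters 28 and completers 23 (section 1): 28 − 23 = 5, which matches the stated exclusions. 5/28 = 17.9%.

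**Checking the reasons against the count.** Metal thread 1 + attitude 1 + hindrance of drawing blood 1 + blood sampling not possible 2 + personal issues 1 = 6. Six separate starters lost would leave 28 − 6 = 22, not 23. The document does not show whether one person carries two reasons or one left before starting. So it is unknown which listed people make up the five, or whether the staff-removed person is among them.

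**What each analysis needs.**
- *Multimodal regression (primary model):* components from brain, blood and behaviour. A day without blood or scan data cannot enter the full model. No random effect is stated.
- *Subjective measures, partial least squares and Bayesian regression:* intake, ratings, time, energy expenditure, weight and BMI. Height and weight are taken at screening, and the endocrine subsection derives energy expenditure from them. Neither blood, scans nor four days are required.
- *Subjective measures, repeated-measures ANOVA:* no blood or scans, but the classical form drops anyone with a missing cell. Fitted as a mixed model, it would not.
- *Endocrine-to-intake regression and nutrient-sensing ANOVA:* both state a subject random effect, so incomplete participants can contribute, but only on days with a blood-marker area under the curve.

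**Days lost.** Completers give 23 × 4 = 92 participant-days. The days provided by the five are not stated, so assume k usable days each, k = 0 to 3. Extra days = 5k, and the share of obtainable days lost = 5k/(92 + 5k).

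**Precision.** Assume a participant random intercept with within-person correlation ρ (0 to 0.9, not given in the documents), and the missing days spread evenly over the four conditions. For a preload main effect coded ±1, a completer contributes information 4/(1 − ρ). A person with k days contributes on average [k − ρk(4 − k)/(3(1 + (k − 1)ρ))]/(1 − ρ). The ratio of the completers-only variance to the all-days variance is therefore

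R = 1 + (5/92) × [k − ρk(4 − k)/(3(1 + (k − 1)ρ))],

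and the standard error falls by 1 − 1/√R.

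| k | Days added | Total days | Share lost now | R (ρ = 0.9 to 0) | Fall in standard error |
|---|---|---|---|---|---|
| 0 | 0 | 92 | 0% | 1 | 0% |
| 1 | 5 | 97 | 5.2% | 1.005 to 1.054 | 0.3% to 2.6% |
| 2 | 10 | 102 | 9.8% | 1.074 to 1.109 | 3.5% to 5.0% |
| 3 | 15 | 107 | 14.0% | 1.146 to 1.163 | 6.6% to 7.3% |

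Worked example, k = 3 and ρ = 0.9: 3 − 0.9 × 3 × 1/(3 × 2.8) = 2.679; R = 1 + 5 × 2.679/92 = 1.146; 1 − 1/√1.146 = 6.6%.

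**The case against.** The strongest reply is that there may be nothing to recover. Nothing in the document says that any non-completer finished a test day. Intake is measured at the end of the day, so a day stopped because blood could not be drawn may have no primary outcome. A reader might infer that usable data are known to be thrown away; the document does not support that, and the point is conditional on such days existing.

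A reader might also infer that the planned models already accommodate incomplete participants. Only the two endocrine models state a subject random effect, and both need blood. Three of the six listed reasons are failures of blood sampling, so where a random effect is stated the affected days may be unusable. The models that do not need blood state no random effect. This stands against any general appeal to mixed models. It does not rescue the four-day rule for the partial least squares and Bayesian regressions on ratings, which do not require four days per person, and the ANOVA can be refitted.

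It is fair, too, that most reasons (blood access, metal thread, scheduling) have no evident link to preload or intake, so bias in the within-person contrasts is not shown. Section 5 itself treats non-compliance as a threat to validity, so whether the staff-removed person belongs in the main set is a matter of judgement. The eligibility criteria sit in a separate document not available here, which may cover some removals.

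**Conclusion.** The point holds as a minor one. The stated set is completers only, it is applied to analyses that do not need it, and no missing-data plan or sensitivity analysis accompanies it. The cost lies between nothing and 15 participant-days (14.0% of obtainable days), and the gain in standard error is at most about 7%. Those bounds assume five people with 0 to 3 usable days each, a random-intercept model, correlations from 0 to 0.9, and missing days balanced over conditions. The full multimodal model would gain only from days that also have blood and scan data.

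The mismatch between 5 exclusions and 6 reasons is a plain inconsistency and does not depend on these assumptions. The missing criterion for the attitude removal is likewise a gap in what is written. A reader might go further and infer that the removal was made with knowledge of that person's intake, or that the results are biased. The document supports neither; it simply does not exclude the first.

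**What to change.** - Define the analysis set separately for each analysis: every participant-day with intake and the regressors that analysis uses.
- Do not require blood or scan data for the partial least squares and Bayesian regression of intake on ratings.
- Fit the repeated-measures ANOVA for ratings and intake as a mixed model so that incomplete participants contribute.
- Let the two endocrine models with a subject random effect use all days with blood.
- Keep the 23 completers as a sensitivity set.
- State the criterion and timing of the staff removal, and show results with and without any available days from that participant.
- Report the number of days available per non-completer, and reconcile the 5 exclusions with the 6 reasons.

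This does not require adding a random effect to the primary multimodal model. The document says data collection is still under way, so the sets can be fixed before analysis. The cost is some wording, modest data handling and refitting one ANOVA. Sample sizes will differ slightly between analyses and must be reported. If no non-completer has a usable day, the data analysed, and hence the results, do not change.

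### The Bayesian regressions of energy intake name no participant term, although intake is measured four times in each of 23 people

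*Combined protocol and SAP*

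**What the plan says.** Section 1 reports "Fully completion of all four test days 23", and section 3 plans to analyse 23 participants. On the primary outcome, energy eaten at the ad libitum meal, section 3 says: "There will be four such measurements per participant, one for each condition".

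Three Bayesian regressions take intake as the dependent variable:

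- *Multimodal metric.* "A Bayesian linear regression will be implemented in JASP software, with the primary outcome of energy consumption as the dependent variable". The regressors are principal components from the brain, blood and behaviour data. The null is defined thus: "The null model is taken to include all covariates not included in the neuroimaging data, subjective report data, or endocrine and metabolite data". Those covariates are not listed. One planned output is: "Bayes factors will also be computed between data modalities, to evaluate the relative importance of each modality in predicting energy consumption".
- *Subjective measures.* "we will perform a Bayesian Linear regression with subjective reports and time as regressors, and with energy expenditure, weight and BMI as covariates".
- *Endocrine responses, item 1.* A regression on area-under-the-curve (AUC) blood markers, whose form is given only by pointing back to a preceding section.

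Other analyses do handle the repeated measurement. The non-Bayesian, marker-by-marker regressions of intake in endocrine item 1 carry subject id as a random effect. The ANOVA under subjective measures, whose responses include intake, says: "The repeatedmeasure factor will be the within-subject factor". The hormone ANOVA in endocrine item 2 also has subject as a random effect.

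The row unit is not stated. For the multimodal model the plan says "The regressors can also be grouped according to timepoint, affording comparison of inclusion probabilities between distant and proximal times to the point of consumption", which suggests one row per person-day with timepoints as separate columns. The subjective regression has time as a regressor, so its rows may be finer than one per day.

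**The concern.** Four intakes from one person are likely to resemble each other. A regression that ignores this makes two opposite errors. For a regressor that is stable within a person, it counts four correlated rows as four independent pieces of evidence, so the Bayes factor is too large. For a regressor that changes from day to day, it leaves the differences between people in the residual, so the Bayes factor is too small. Because the errors run in opposite directions, no single discount repairs the results.

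The stakes are highest in the multimodal analysis. It compares three data types that may differ in how stable they are within a person, and it serves what section 5 (Limitations and Caveats) calls the main goal. Section 5 also counts on intake varying both between and within people, and between-person variation is the condition under which the problem arises.

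**Working it through.** **Inputs from the documents.** 28 started and 5 were excluded (section 1): 28 − 5 = 23. Each gives four intakes (section 3): 23 × 4 = 92 values in 23 clusters of 4. The plan states no power, alpha or ICC figure, so there is none to reproduce.

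**Assumptions, none from the documents.** ICC of intake 0 to 0.7; ICC of the regressor 0 to 1; cut-off BF > 3; JZS prior with scale 0.354. In steps 3 (median BF) and 4, a true effect explains 12% of within-person intake variance. "No participant term" below means 92 rows treated as independent.

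**1. Design effect, regressor with no effect.** DE = 1 + (4 − 1) × ICC(intake) × ICC(regressor). Effective n = 92 / DE. False-positive rate at nominal two-sided 5% = 2 × [1 − Φ(1.96/√DE)]. For example, at 0.3 and 0.5: DE = 1 + 3 × 0.3 × 0.5 = 1.45 and n = 92/1.45 = 63.4.

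| Regressor ICC | Intake ICC | DE | Effective n | Formula | Simulated |
|---|---|---|---|---|---|
| 0.5 | 0.3 | 1.45 | 63.4 | 10.4% | 10.2% |
| 0.5 | 0.5 | 1.75 | 52.6 | 13.8% | 13.7% |
| 0.5 | 0.7 | 2.05 | 44.9 | 17.1% | 16.8% |
| 1 | 0.3 | 1.90 | 48.4 | 15.5% | 15.6% |
| 1 | 0.5 | 2.50 | 36.8 | 21.5% | 22.0% |
| 1 | 0.7 | 3.10 | 29.7 | 26.6% | 27.9% |

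At regressor ICC 0, DE = 1 and the rate stays near 5%. With participant accounted for, the simulated rate is 4.8–5.1% in every setting (20,000 data sets each).

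**2. The same on the Bayes factor scale.** With 92 rows and one regressor, BF > 3 corresponds to R² above 0.063. Chance of BF > 3 for a regressor with no effect and no participant term, also when null-model covariates absorb part of the between-person intake variance:

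| Intake/regressor ICC | None absorbed | 60% absorbed | 80% absorbed |
|---|---|---|---|
| 0.3/0.3 | 3.1% | 2.3% | 2.1% |
| 0.5/0.5 | 6.6% | 4.5% | 2.9% |
| 0.5/0.8 | 10.5% | 6.2% | 4.2% |
| 0.7/0.8 | 14.5% | 10.6% | 7.1% |

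With a participant intercept the chance is about 1–3%. At intake ICC 0 it is 1.6% without one, so there is no inflation.

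**3. A true regressor that varies only within a person.** With no participant term, the median BF is 41, 24, 8.3, 3.0 and 1.1 at intake ICC 0, 0.1, 0.3, 0.5 and 0.7. With a participant intercept it is clearly higher once intake ICC is appreciable. The exact value depends on how the prior is scaled to the clustered design, so no single figure is given. Power needs no prior and shows the same direction. With slope 0.2, regressor SD 1 and total residual SD 1, it is 0.47, 0.48 and 0.48 at intake ICC 0.3, 0.5 and 0.7 without a participant term, against 0.50, 0.63 and 0.83 with one.

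**4. Ranking of modalities (multimodal model only).** Assumed: three modalities with two components each, so 2⁶ = 64 equally likely models, and one true component. The figures are the chance that the true modality is not ranked first, at intake ICC 0.3/0.5/0.7.

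- Mild case (equal stability, same slope between and within people, 60% absorbed): 2/5/16%, against 2–5% with a random intercept.
- Severe case (null modalities more stable, 0.8 against 0.2, effect within person only): 29/47/64%, against 9–10%.

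The comparators again depend on prior scaling. The plan keeps as many components as explain 95% of the variance, so two per modality is only an illustration.

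**5. Copied outcome (subjective regression only, if rows are rating times).** Assumed: four timepoints, and report variance split 30% person, 30% day and 40% timepoint. A regressor with no effect reaches BF > 3 in 19–27% of trials at intake ICC 0.3–0.7, and in 12% even at ICC 0. A participant intercept alone leaves 9–10%, so it does not cure copying.

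**The case against.** The best reply is that the plan is incomplete rather than wrong. Nowhere does it say that rows are independent. For the multimodal model this stands: the null model holds unlisted covariates, and participant could be among them. A reader might infer that the plan commits to a wrong model there, but the text supports only under-specification. The reply does not help the subjective regression, which lists its covariates without participant.

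A second reply is that the endocrine cross-reference may mean the regression just before it, which has subject id as a random effect. That regression is not called Bayesian and sits in the same section and item, so it is the weaker candidate. The multimodal and subjective sections both describe Bayesian regressions, and neither names a participant term. The reference still has to be resolved.

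A third reply is that person-level covariates such as weight absorb between-person variance. This stands in part: step 2 shows inflation shrinking as more is absorbed, but still 2.1–7.1% at 80%.

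Two stronger readings go too far. One is that the primary analysis is invalid: the multimodal model uses the primary outcome, but no section labels it the primary analysis. The other is that the modality ranking will be wrong: step 4 runs from negligible harm to large.

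**Conclusion.** The point holds. The subjective regression omits participant from a stated list. The multimodal regression does not name it. The endocrine Bayesian regression most naturally inherits the gap. All three concern an outcome with 92 values in 23 clusters, for which the plan uses a subject or within-subject term elsewhere.

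The harm is conditional on intake differing between people after the covariates. Given that, evidence is too strong for person-stable regressors: about 3–15% of null regressors pass BF > 3 over the assumed ICC range with no absorption, against about 1–3% with a participant intercept. Evidence is too weak for within-person regressors: the median BF falls from about 40 at intake ICC 0 to about 1 at 0.7. The omission is certain for the subjective regression. The size of the harm is not, because the ICCs, effect size, prior scale, component count and cut-off are all assumed.

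**What to change.** - In all three Bayesian regressions, include a participant intercept in every model, including the null. Make it random, as in the marker-by-marker endocrine regressions, or fixed if only within-person prediction is wanted. Use software or a module that supports this.
- List the null-model covariates of the multimodal regression.
- Use one row per person-day, so that each intake value enters once. In the subjective regression, enter ratings at different times as separate regressors or summaries. Merely disclosing that intake is copied across rows would not remove the error.
- Name the section to which the endocrine cross-reference points.
- Consider the same clustering in the Partial Least Squares analysis of intake, for example by centring within participant or resampling by participant.

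The cost is plan wording and somewhat more modelling. Evidence for between-person predictors will be weaker, because it rests on 23 people. Section 3 says data collection was not finished, so the change can be fixed in advance.

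### The plan asks how well appetite ratings and hormones predict intake but schedules no out-of-sample check; the resulting excess in R² ranges from small to large, depending on partial least squares choices left open

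*Combined protocol and SAP*

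**What the plan says.** Under Statistical modelling of subjective measures, the question is "how well subjective measures predict energy intake". The answer is a PLS analysis "to find the multidimensional direction in appetite sensation space" with the property "that explains the maximum variance in energy intake space". The number of components, the number of rating columns, the layout of ratings by time and the handling of four days per person are not stated. The same section adds a second analysis: "To isolate the subset of subjective factors that are best predictive of energy intake we will perform a Bayesian Linear regression".

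Under Statistical modelling of endocrine responses, item 1, the same question is put for hormones. One regression is run per marker, on its area under the curve (AUC), with energy expenditure as covariate and a random subject effect, "to find the marker that explains the maximum variance in energy intake". A further analysis follows: "we will perform a Bayesian linear regression (as described in preceding section), with energy intake as dependent variable". Its markers are listed as "including GLP1, Ghrelin, PYY, CCK, glucose, insulin", so there are at least six.

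On numbers, Outcome Measures says: "There will be data analysed from 23 participants". Each has four intake measurements, one per condition. No section mentions cross-validation, a hold-out set, permutation or any other correction for optimism.

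**The concern.** A question about how well something predicts is answered by performance in data that did not shape the model. Here PLS weights are chosen to fit intake, and the leading hormone is chosen because it fits intake best, in the same 92 person-days (23 × 4) that supply the R². Such an R² tends to be too high, and adding PLS components can never lower it. It therefore cannot be used to choose the number of components, nor can it warn that a fit is noise. Prediction of satiety is the main goal named under Limitations and Caveats, so these R² values bear on the study's purpose.

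**Working it through.** The plan gives no R², power or optimism figure to reproduce, so the size was found by simulation.

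**Inputs from the documents:** 23 participants; 4 days each; PLS on ratings; six named markers; one marker per model plus energy expenditure and a random subject effect.

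**Assumed, because not stated:** one row per test day; intraclass correlation (ICC) 0.5; 8–40 equally correlated rating columns; 1–3 components. A second layout used 24–48 rating-by-time columns (4–8 ratings × 6 times) with ICC 0.3–0.5.

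**Measure:** held-out R² = 1 − (squared error when all four days of a participant are left out) / (squared error of the training mean).

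**PLS, no true association.** Typical in-sample R²; the held-out value is below zero in every row.

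| Columns | Components | Correlation | In-sample R² |
|---|---|---|---|
| 8–40 ratings | 1 | 0.5–0.7 | 0.04–0.10 |
| 20–40 ratings | 1 | 0.3 | 0.15–0.19 |
| 20–40 ratings | 1 | 0.2 | 0.20–0.27 |
| 20–40 ratings | 1 | 0 | 0.25–0.39 |
| 8 ratings | 2–3 | 0–0.7 | 0.11–0.14 |
| 20–40 ratings | 2–3 | 0–0.7 | 0.25–0.54 |
| 24–48 rating-by-time | 1 | 0.7–0.8 | 0.07–0.10 |
| 48 rating-by-time | 1 | 0.5 | 0.17–0.20 |
| 24–48 rating-by-time | 2–3 | 0.7–0.8 | 0.15–0.32 |
| 48 rating-by-time | 2–3 | 0.5 | 0.30–0.43 |

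Repeat runs moved these values by up to about 0.03.

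**PLS, one shared factor explaining 20% of intake, rating correlation 0.5.** The R² attainable with unlimited data and k ratings is 0.20 × 0.5k / (1 + 0.5(k − 1)).

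- k = 8: 0.20 × 4 / 4.5 = 0.178. One component: 0.20 in-sample, 0.13 held out.
- k = 20: 0.20 × 10 / 10.5 = 0.190. One component: 0.22 and 0.16.
- k = 40: 0.20 × 20 / 20.5 = 0.195. One component: 0.23 and 0.16.

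In-sample R² exceeds the attainable value by 0.022, 0.030 and 0.035. The rest of the gap to the held-out value (0.048, 0.030 and 0.035) is the loss from estimating the direction in a small sample. With two components the in-sample value is 0.26–0.52 and the held-out value 0.00–0.06 across runs.

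**More components are not always worse.** When a second dimension truly matters (20% signal), held-out R² for one, two and three components is 0.09–0.12, 0.14–0.17 and 0.01–0.08. In-sample R² is nevertheless highest at three.

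**Hormones, best of six by marginal R²** (fixed effects only), energy expenditure in the model but assumed to have no true effect:

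- no marker effect: 0.06–0.07 in-sample, -0.05 to -0.07 held out;
- true marker R² 0.10: 0.12–0.13 in-sample, 0.01–0.04 held out.

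Most of the no-effect gap is not selection. In a separate run at ICC 0.5, scored in new simulated participants, the model with energy expenditure alone gave 0.031 in-sample and -0.065 in new people, a gap of 0.096. Adding the chosen marker changed these by +0.032 and -0.035, a further 0.067. For within-person R², one null marker fixed in advance gives 1/(92 − 23) = 1/69 = 0.014, while the best of six gives 0.036–0.043.

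**Ranking of markers** (run without the energy-expenditure covariate, so indicative only): the true marker came first in 44–56%, 61–79% and 82–95% of datasets at true R² 0.05, 0.10 and 0.20.

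**The case against.** The strongest reply is that the plan, read plainly, does little harm. It speaks of one direction, which suggests one component, and appetite ratings are likely to be correlated. The bias is then 0.02–0.04, against a 5–95% sampling range of about 0.08–0.40 for in-sample R² in the 20% signal case. The large figures need choices that the plan has not made. This stands, and it keeps the point from being a fatal one. It does not settle the matter, because the number of components and the column layout are open. Even one component gives 0.17–0.20 from noise with 48 rating-by-time columns correlated 0.5.

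A second reply is that the R² values would not stand alone, since Bayesian regressions are planned on the ratings and on all marker AUCs. If the endocrine one follows the multimodal description, models can be compared with a null, which penalises complexity. That is a real safeguard for judging which regressors matter. It does not adjust the PLS R² or the best-marker R².

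A reader might infer more: that the study will report grossly inflated prediction, that the hormone result is mainly a selection artefact, or that the multimodal model shares the fault. The documents do not support these readings. They never say that an in-sample R² will be presented as predictive accuracy, and they do not commit to several components. The hormone excess is modest, and much of its gap to held-out R² is small-sample estimation loss. The multimodal model uses a different procedure and is not part of this point.

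**Conclusion.** The concern holds in graded form and should be addressed. Two questions about prediction are answered by fit to the same 23 × 4 data, with no out-of-sample check. The excess is small for one component on ratings correlated 0.5–0.7 and modest for hormones. It is large for two or three components on 20–40 ratings, where a quarter to a half of intake variance can appear explained by noise. It is intermediate for weakly correlated ratings or many rating-by-time columns. With about 8 ratings it stays at 0.11–0.14 even with two or three components.

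The omission is certain from the text. The sizes are conditional on the assumed ICC, correlations and column counts. The hormone figures further assume marginal R², which the plan does not specify. Conditional R², which counts the subject effect as explained, would be about 0.29–0.69 with no hormone effect at all.

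**What to change.** Set the number of PLS components and the column layout in advance, or choose the number of components by inner cross-validation. For the PLS and the single-marker models:

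- report leave-one-participant-out R² beside the in-sample R², and label the latter as in-sample;
- hold out all four days of a participant together;
- repeat scaling, component choice and marker selection within each fold;
- predict from fixed effects only, and say that the hormone R² is marginal;
- report R² for every marker, not only the top one.

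State that this measures prediction for a new person. If prediction across days within a person is also of interest, a permutation of intake within participants and a participant-level bootstrap are optional additions.

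The cost is 23 refits per model and no new data; the plan describes data collection as unfinished, so the change can still be specified beforehand. The reported explained variance will be smaller. Choosing components by inner cross-validation gave 0.01–0.06 less held-out R² than the best fixed number in the simulations.
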